6.1.3 Method of Assignment/Randomization (if applicable)

NA

6.1.4 Blinding and Procedures for Unblinding (if applicable)

Participants will not be blind to behavioral and medication treatments. There is no placebo for this trial because NB is an evidence-based weight loss treatment.

6.1.5 Packaging/Labelling

Refer to medication package insert.

6.1.6 Storage Conditions

The medication will be stored and dispensed at the Yale Investigational Drug Services pharmacy.

6.2 Assessments

Assessment Procedures. **Table 1** summarizes the assessment schedule and measures. Assessments will be done by *independent* evaluators *not* involved in the treatment delivery and *blind* to early weight loss responder status.

Assessment of Treatment Outcome and Time Course.

Percent total weight loss (%TWL) (measured weight across time points). Per standard reporting guidelines, %TWL will be determined by the following formula: [(Initial Pre-Treatment Weight) — (Post-Treatment Weight)] / [(Initial Pre-Treatment Weight)]*100.

Psychosocial/Behavioral Functioning listed below.

Informed consent will be obtained after complete study description, followed by interviews and surveys.

Interviews:

Eating Disorder Examination Interview — Bariatric Surgery Version (EDE-BSV) (18) an investigator-based interview will be the primary method for assessing loss-of-control eating, as well as severity of eating-disorder psychopathology.

Mini International Neuropsychiatric Interview-Version 7.0 (MINI) (19) is a brief structured interview for psychiatric disorders, which will provide data to characterize subjects.

Anthropometrics: **Weight** and **height** will be measured to calculate body mass index.

Self-Report Measures (baseline and repeated per Table 1):

Demographics: ethnicity/race, age, sex, education, and socio-economic status.

Eating Disorder Examination-Questionnaire Version with Instructions (EDE-Q-I) (20), which generates the same eating behavior and pathology data as the interview version, will be used across *all assessment points* given its low burden (*in addition to the EDE-BSV given during major assessment points*).

Food Craving Inventory (FCI) (21) assesses general and specific food cravings (**relevant for NB**) and comprises four subscales for different food groups. The FCI has been validated and psychometrically supported in studies with obesity and BED. The use of this craving instrument will allow direct comparison to the leading NB non-surgical obesity trials (14).

Patient Health Questionnaire-9 (PHQ-9) is a brief and widely-used measure of depression in diverse medical settings (22). Post-MBS depression was associated with poorer MBS outcomes in some studies and is relevant to the study medication.

Treatment Variables: Credibility ratings will be examined before beginning treatments and again after completing treatments. Treatment Compliance for BWL will include session attendance and self-monitoring compliance and counts, and pill count method for medication.

Adverse Events will be collected during clinic visits using adverse event checklist of the most commonly reported adverse events for NB to monitor safety.

6.2.1 Efficacy. NB is an FDA-approved medication for weight loss among individuals with obesity.

6.2.2 Safety/Pregnancy-related policy

Given the uncertain effects of medication during pregnancy, the following precautions will be taken for women of reproductive age who are sexually active and non-responders (those who will be starting NB medication) : 1) a pregnancy test will be required; 2) will be required to use a reliable method of birth control while she is in the study and to alert the research team if she departs from her birth control plans or if, in spite of adherence to these plans, she thinks she might be pregnant, and 3) if a woman becomes pregnant after study entry, her medication will be discontinued.

6.2.2.1 Adverse Events Definition and Reporting

Adverse event data will be collected on an on-going basis. Adverse events data will be reviewed by the PI and co-investigators throughout this trial. A summary of adverse events will be provided to the Yale IRB yearly during the annual renewal review process. Any serious or unanticipated adverse events will be reported to the Yale IRB within 48 hours.

6.2.3 Pharmacokinetics (if applicable)

6.2.4 Biomarkers (if applicable)

6.3 Study Procedures

Subjects will participate in an initial evaluation to determine eligibility. Eligible participants who provide written informed consent will start BWL treatment which last for three months. The BWL treatment is a mixture of the published LEARN behavioral lifestyle weight control treatment developed by Brownell (2000) and the Diabetes Prevention Program (Knowler et al., 2002); the PI and research team has extensive experience administering BWL with patients with obesity, binge-eating disorder, and histories of bariatric surgery. BWL will be delivered weekly by research-clinicians according to treatment manuals that detail session-by-session procedures. These manuals closely parallel patient-version BWL self-care materials for the entire course of treatment and follow closely that used by Wadden et al. (2011) in the COR-BMOD Trial testing BWL and NB/placebo medication for obesity, but modified for post-MBS patients. Behavioral strategies (goal-setting, self-monitoring, stimulus control problem-solving) will be taught within a lifestyle approach for achieving dietary goals (augmented by portion size and caloric goals) and physical activity goals (to achieve 180 min/week of moderate physical activity). Research-clinicians will be trained in BWL by the research team and will be supervised and monitored over the course of treatment delivery to ensure quality adherence. After one month of BWL treatment, "treatment response" will be determined based on early weight loss status because of its strong prognostic significance for optimal weight loss outcomes. Early weight-loss responders will continue BWL treatment, while *non*-responders will be given a pharmacologic agent (NB) to augment BWL treatment for the remaining two months of treatment. Outcomes assessments will be done by independent evaluators not involved in the treatment delivery and blind to responder status. Participants will be asked to complete self-report surveys at the baseline evaluation, monthly during treatment, and at the end of treatment. For participants starting NB medication, they will be asked to have labs drawn to examine liver values for safety before starting medication and again after being on the medication for one month.

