6.3.1 Study Schedule

Assessment Points	Baseline	during rx 1-Month	during rx 2-Month	POST rx 3-Month
Medical History, Height, MINI Psychiatric Interview, Demographics (i.e., sex, race)	■			
EDE-BSV Interview, Treatment Credibility/Satisfaction	■			■
EDE-Q-I, FCI, PHQ-9, GPAQ, Weight, Adverse Events, Compliance	■	■	■	■

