6.3.6 End of Study and Follow-up

Participants will be asked to attend a post-treatment (end of study) assessment, which will consist of an interview, measured weight, and completion of self-report surveys as indicated in the assessment schedule grid.

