6.3.7 Removal of subjects

Withdrawal/attrition from treatments will be examined. Use of other treatments during the study will be assessed and considered in analyses. Patients will be asked about all forms of treatments during major assessments. Criteria for removal of patients from the study may include worsening depression, suicidal ideation, or failure to comply with medication. Previous experience suggests that worsening clinical status is rare; in such cases, [name] and study physician would determine whether to remove the person from the study and provide referrals.

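### Do the scheduled weight, pill-count and treatment-use items defeat the stated blinding of outcome evaluators to responder status?

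*Combined protocol and SAP*

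**What the plan says.** Blinding of evaluators is stated twice. Section 6.2 says of Table 1 that it "summarizes the assessment schedule and measures. Assessments will be done by" independent evaluators who do not deliver treatment and are blind to early responder status. Section 6.3 says: "Outcomes assessments will be done by independent evaluators not involved in the treatment delivery and blind to responder status".

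The items that bear on this are:

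- The row of Table 1 (6.3.1) marked at baseline and at months 1, 2 and 3 reads "EDE-Q-I, FCI, PHQ-9, GPAQ, Weight, Adverse Events, Compliance".
- On compliance, 6.2 says: "Treatment Compliance for BWL will include session attendance and self-monitoring compliance and counts, and pill count method for medication".
- On treatment use, 6.3.7 says: "Patients will be asked about all forms of treatments during major assessments".
- Section 6.2 describes the self-report EDE-Q-I as used at every point, "in addition to the EDE-BSV given during major assessment points". Table 1 puts the EDE-BSV at baseline and month 3.
- Section 6.3.6 describes a single end-of-study assessment, "which will consist of an interview, measured weight, and completion of self-report surveys as indicated in the assessment schedule grid".
- Section 6.1.4 says: "Participants will not be blind to behavioral and medication treatments". It adds that there is no placebo.

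**The concern.** Read with the blinding sentence in 6.2 covering every row of Table 1, the evaluators would handle three kinds of information that point to responder status: the month-1 weight from which status is set, a pill count that exists only for non-responders, and answers about treatment from participants who know what they are taking. The plan gives no order of items within a visit, no split of tasks by role, and no check on whether the blind held.

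The EDE-BSV is the outcome at stake. It is rated by the interviewer and is the main instrument for loss-of-control eating. Its baseline rating comes before responder status exists, so any expectation held by the month-3 rater would enter the change score directly. Section 1.1 intends within-group psychosocial change in the combined condition to supply effect sizes for later trials. A report that repeated the blinding statement might then claim more than the conduct delivered.

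**Working it through.** No figure in the plan depends on this point, so the check sets the sections side by side.

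**How much is exposed (Table 1, with 6.1.2 and 6.3).**

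| Item | Points listed | Points at which it could bear on status |
|---|---|---|
| EDE-BSV | 2 of 4 (baseline, month 3) | 1 (month 3) |
| Weight | 4 of 4 | months 1 to 3, by inference only |
| Pill count, within compliance | compliance at 4 of 4 | at most 2 (months 2 and 3), since NB starts after month 1 |
| EDE-Q-I (self-report) | 4 of 4 | none; not rated by an interviewer |

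**Weight.** Status is set after the month-1 weight is taken, so whoever takes that weight does not yet know it. To infer status later, an evaluator would need the baseline weight, the month-1 weight and the cut-off. Section 2.1 reports early losses of 0.5 to 3%, and at least 1%, from earlier work, but no section adopts an operative cut-off. The plan speaks of evaluators in the plural and does not say that one person covers all visits. Weight can suggest status; it does not disclose it.

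**Pill count.** This is the strongest strand. With no placebo, having pills to count identifies a non-responder. But no section gives the count to the EDE-BSV interviewer. Section 6.1.2 describes brief physician visits concerned with dosing compliance and side effects. Session attendance and self-monitoring, the other parts of compliance, arise in treatment sessions. Table 1 also marks compliance at baseline, before there is any treatment to comply with. The row is therefore better read as scheduling shorthand than as a list of one evaluator's tasks.

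**Treatment questions.** In 6.3.7, the sentence just before the quoted one is about use of other treatments during the study, so the natural subject is non-study treatment, although the quoted words are wider. The section does not say who asks.

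**Other staff in contact with participants.** Section 3.3.1 has research clinicians review the PHQ-9 at monthly clinic visits. Section 6.2 has adverse events collected at clinic visits. The adverse-event checklist does not itself reveal status, since Table 1 lists adverse events for everyone from baseline.

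**What the blind protects.** A rater fully blind to responder status could still know that the month-3 interview is post-treatment and that every participant received active treatment. General before-and-after expectation would therefore survive a perfect blind. Blinding to status chiefly guards the comparison of responders with non-responders, and those groups are formed by early response, not by randomisation. What remains for the within-group change is any extra expectation tied to NB, of unknown size and direction. Section 6.4.1 specifies models for percent weight loss only, so no planned analysis of the EDE-BSV would be altered.

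**The case for a change.** The best case for a change is that the blinding claim in 6.2 has no exception by item and directly follows the reference to Table 1. Narrowing it to the outcomes wording of 6.3 does not help, because 5.2.1 counts both compliance and weight among the primary outcomes. Section 6.1.2 says what physician visits focus on but does not assign the pill count to the physician. Interviews are recorded (7.7), yet no blinded re-rating is described. Confounding of the between-group contrast does not excuse rater bias in the within-group change, and writing down roles and visit order would cost little.

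Much of this stands as description. The plan does not say who counts pills or who asks about treatment, and independence from treatment delivery is the only protection it states. If the month-3 interviewer did either task before rating, that rating should not be reported as blinded. It does not follow that the procedures contradict the blind. That conclusion requires one person to hold all the tasks, which no section says. Carrying out the plan as written includes keeping the evaluator blind, and that already requires someone else to do the revealing tasks, or to do them after the interview.

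**Conclusion.** The concern does not call for a change. It identifies missing operational detail that a study team would ordinarily settle in its visit procedures, and no break of the blind is shown. At most one of two ratings of one secondary, interviewer-rated outcome is exposed, in an open-label, non-randomised, single-site pilot of 25. Measured weight and the self-report scales do not depend on an interviewer's rating, and 6.2 says the EDE-Q-I, collected at all four points, yields the same eating-behaviour and pathology data as the interview.

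This rests on two assumptions: that staff honour the stated blind when tasks are allocated, and that the sentence in 6.3.7 is mainly about non-study treatment. If the first failed, the consequence would be for reporting: the month-3 EDE-BSV could not be called blinded. The planned weight analyses would be unaffected.

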Risks. Several large-scale studies have found that this medication is safe and effective for the treatment of obesity [Rusch & Andris, 2007; Elder et al., 2008; Mond et al., 2010; Citrome, 2015]. The NB combination approved by the FDA (Contrave) is reported to have the following common adverse reactions: nausea (32.5%), constipation (19.2%), headache (17.6%), vomiting (10.7%), dizziness (9.9%), insomnia (9.2%), dry mouth (8.1%), and diarrhea (7.1%). In addition, Contrave will have the FDA warnings and precautions: Suicidal Behavior and Ideation: Monitor for depression or suicidal thoughts. Discontinue medication if symptoms develop. Risk of seizure may be minimized by adhering to the recommended dosing schedule and avoiding co-administration with high-fat meal. Increase in Blood Pressure and Heart Rate: Monitor blood pressure and heart rate in all patients, especially those with cardiac or cerebrovascular disease. Hepatotoxicity: Cases of hepatitis and clinically significant liver dysfunction observed with naltrexone exposure. Angle-closure glaucoma: Angle-closure glaucoma has occurred in patients with untreated anatomically narrow angles treated with antidepressants. Use of Antidiabetic Medications: Weight loss may cause hypoglycemia. Monitor blood glucose. Warning about Opioid Withdrawal: We will include this advisory pertaining to opioid use and examples of opioid-based medications and drugs in the written consent form as well as the verbal consent process: *Naltrexone can cause withdrawal symptoms in individuals who are taking opioid pain medications or drugs. You should not participate if you are taking opioid medications of any kind and we will not include you in the study if we know or suspect you are using opiate-containing drugs.* In addition to structured clinical diagnostic interviews with our clinical-research staff and medical record reviews, we will perform lab urine test at Quest with potential subjects suspected of opiate usage.

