In the proposed RCT, our dosage follows standard and long-standing dosage for both naltrexone and bupropion used for related psychiatric problems. Per previous RCTs, a dosing escalation approach will be used [Greenway, Fujioka & Plodkowski, 2010; Wadden et al., 2011]. This dosing will continue for the remainder of the RCT unless a patient develops intolerable side effects. If such occur, the physician may reduce the dosing to achieve tolerability. If the patient cannot tolerate the medication, has adverse effects, or is non-compliant with medication for >7 consecutive days, they will be discontinued from the medication. Physician visits will be brief (10 -15 minutes), focusing on compliance with dosing and evaluating side effects. For participants taking medication for greater than 4 weeks, a 7-day taper will be provided.

Month 2	NB Medication	
Study Day	Naltrexone Capsule	Bupropion IR Capsule
1-7	--	150 mg once a day
8-study end	50 mg	150 mg twice a day

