Participation rates (retention and attrition) will be reviewed on an ongoing basis by the PIs and co-investigators to identify any potential problems, and formally twice-yearly. Any differential dropout and/or higher than expected dropout will be reviewed by the investigators to determine whether any problems are present and what, if any, corrective action needs to be taken.

During the reviews, if the investigators have concerns about whether attrition has reached a level that might inhibit the ability of the study to address its primary aims, they will suggest a meeting to discuss methods for improving subject retention. Previous pharmacotherapy studies for binge-eating disorder and obesity (with comparable time frames for pharmacotherapy) have reported attrition rates between 20% and 38%. Studies of NB for obesity treatment reported attrition of 30% to 45%. Thus, "trigger points" for review and discussion by principal investigator and research staff will be: 35% ("low alert"), 40% ("mid alert"), 45% ("high alert"), 50% ("extreme alert"). With early alerts to problems, action would be taken to avoid higher level alerts; if a higher level alert should arise, more drastic actions would be taken.

Trial Stopping Rules

Given that this study is deemed greater than minimal risk to human subjects, it is more likely that attrition or difficulty in recruiting adequate numbers of participants will require stopping the trial than would excess adverse events. However, as outlined, adverse events will be monitored in all participants, and the PI will alert the Yale IRB and the APF if a larger (or more serious) than reasonably expected adverse event rate should occur. Other potential issues relating to stopping rules for this trial include:

1. New Information

It is unlikely that any new information will become available during this trial that would necessitate stopping the trial. If new safety data (i.e., pertaining to short-term use of the study medication) become available, this will be evaluated.

1. Limits of Assumptions

It is possible that excessive attrition and/or missing data could limit the value of data analysis. This will be evaluated yearly and if present, considered in relation to potential effects on the power to detect differences in the primary outcomes.

The following actions would be taken at each level of alert:

- (1) Low-level alert = Review of potential problems by PI.

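### The only liver measurement scheduled after exposure depends on a month on NB, so participants taken off NB sooner have no scheduled post-exposure liver value

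*Combined protocol and SAP*

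**What the plan says.** Section 6.3 (Study Procedures) is the only place that schedules liver tests. Participants starting NB are asked to have "labs drawn to examine liver values for safety before starting medication and again after being on the medication for one month". NB is given "to augment BWL treatment for the remaining two months of treatment", so planned exposure is about two months.

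Section 6.1.2 sets out when the drug is stopped: "If the patient cannot tolerate the medication, has adverse effects, or is non-compliant with medication for >7 consecutive days, they will be discontinued". Other sections add routes off it: severe side effects (3.3.1), pregnancy (6.2.2) and removal from the study (6.3.7). Section 6.1.2 also allows a middle course, in which "the physician may reduce the dosing to achieve tolerability". Its dosing table gives bupropion alone on days 1 to 7 and adds naltrexone from day 8.

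The hazard is acknowledged. Section 3.3.1 lists hepatotoxicity among the less common NB side effects, and the warnings in 6.1.1 state: "Cases of hepatitis and clinically significant liver dysfunction observed with naltrexone exposure".

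The assessment schedule in 6.3.1 (Table 1) has no laboratory row and no visit tied to stopping NB. The statistical section (6.4.1) covers percent weight loss only.

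**The concern.** Whether the second liver value is due depends on the participant still taking the drug, and staying on the drug depends partly on tolerating it. The value is therefore not scheduled for a group defined by what happened to them after exposure. Two things are at stake.

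- **Individual safety.** A laboratory abnormality in someone who stopped early would be found only if somebody ordered an unscheduled test.
- **Completeness of the safety record.** Section 7.12 has adverse events reviewed quarterly and again as each participant finishes, to decide whether the protocol or consent form needs changing. Section 7.18 has them posted with the results, and the data are meant to inform larger trials. If the record says only that no abnormal liver values were seen, a reader cannot tell how many of those exposed were tested.

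**Working it through.** **Step 1. Is another post-exposure liver test scheduled anywhere?**

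| Provision | Section | Does it schedule a liver value after early stopping? |
|---|---|---|
| Draw before NB | 6.3 | No; precedes exposure |
| Draw after one month on NB | 6.3 | No; requires a month on NB |
| Eligibility laboratory studies | 5.3.2 | No; precede exposure, liver values not named |
| Adverse event checklist | 6.2 | No; covers commonly reported NB events and is not a laboratory test |
| Medical monitoring at visits | 7.12 | Liver test neither named nor excluded |
| Table 1 | 6.3.1 | No laboratory row |

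Table 1 is weak evidence taken alone, because it also omits the eligibility laboratory studies and the pregnancy test. The finding rests on the wording of 6.3 set beside the stopping rule in 6.1.2.

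**Step 2. How many people?** The plan gives no figure to reproduce: it states N=25, but neither how many will start NB nor how many will stop in the first month. Both are assumed here.

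- NB starters: 10, 15 or 20 (40%, 60% or 80% of 25).
- Share stopping in month one: 10% to 30%. For orientation, 7.12 cites attrition of 20% to 38% in pharmacotherapy studies of comparable length and 30% to 45% in NB obesity studies. If half of that fell in month one, the shares would be 0.20 × 0.5 = 10% to 0.38 × 0.5 = 19%, and 0.30 × 0.5 = 15% to 0.45 × 0.5 = 22.5%. Two thirds of the highest figure gives 0.45 × 2/3 = 30%. These are attrition figures from other studies, not rates of stopping NB within a month, so the range remains an assumption.

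Expected number without a scheduled post-exposure value = starters × share stopping:

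| Starters | 10% stop | 20% stop | 30% stop |
|---|---|---|---|
| 10 | 1 | 2 | 3 |
| 15 | 1.5 | 3 | 4.5 |
| 20 | 2 | 4 | 6 |

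The chance that at least one person is affected is 1 − (1 − p)^n, assuming independent stops: 1 − 0.9^10 = 65% at the low corner, 1 − 0.8^15 = 96.5% in the middle and 1 − 0.7^20 = 99.9% at the high corner.

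**Step 3. What would a summary lose, if one were made?** With no abnormal values among n tested, the one-sided 95% upper bound is 1 − 0.05^(1/n). For 15 starters all tested it is 1 − 0.05^(1/15) = 18.1%. With 3 untested it is 1 − 0.05^(1/12) = 22.1%, and that bound carries over to all starters only if the untested resemble the tested. The loss of precision is modest; the missing individual values matter more.

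**Step 4. Exposure at the second draw.** Taking the dosing table's days as counted from the start of NB, naltrexone begins on day 8, so a one-month draw reflects about three weeks of naltrexone. Someone who stops in days 1 to 7 has, by schedule, taken none. Since the warning quoted above refers to naltrexone, those early stoppers need a separate line in any count.

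**The case against.** **No hepatic result is defined.** Primary outcomes are feasibility, acceptability and weight (5.2.1), secondary outcomes are psychosocial (5.2.2), and 6.4.1 analyses weight only. The liver draws are individual monitoring. This stands. A reader might infer that the trial will report a biased hepatic safety result, but no such result is planned. The selection matters for a summary only if one is made; the gap in individual monitoring exists either way.

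**Early stoppers are not left unexamined.** A reader might infer that they are never tested. The documents do not support that. Every NB starter is asked for a draw before the drug, adverse events are collected at the 2-month and 3-month visits, and an unscheduled test is not excluded. What holds is narrower: no liver test is scheduled for them after exposure.

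**Those who reach one month are not simply those who tolerated NB.** Some will be on a reduced dose, and some early stops will be for non-compliance or pregnancy. This also stands; the link to tolerability is partial.

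**The untested are not shown to be at higher risk.** A reader might reason that nausea and vomiting, which can lead to stopping, may also signal liver injury. The documents list these effects separately from hepatotoxicity and do not connect them. They also give no rate of liver abnormality, so any figure for how far detection would fall would come from the assumptions chosen.

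**One month may have been meant as a calendar point.** Possibly, but the text speaks of being on the medication, so it needs clarifying in either case.

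**Conclusion.** The point holds in limited form. As written, participants taken off NB within the first month have no scheduled liver value after exposure, for a hazard the protocol names. The scheduled post-exposure values will come only from people still on NB at one month. Under the assumed 10 to 20 starters and 10% to 30% early stops, that leaves roughly 1 to 6 people without a value; the documents supply neither input. The documents do not show that anyone goes wholly untested, that a hepatic result will be biased, or that the missing values are the abnormal ones. This is a gap in safety data collection that is worth closing because it is cheap to close. It does not affect the weight analysis.

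**What to change.** Reconcile 6.1.2 and 6.3 so that the plan states what happens to the second liver measurement when NB stops early. As a matter of data collection:

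- In 6.3, define the second measurement for everyone who started NB, whether or not they are still taking it. The existing 2-month visit is a natural place: NB begins after month one, so that visit falls about a month after the start. The stopping rule reads "non-compliant with medication for >7 consecutive days, they will be discontinued from the medication", not from the study, so those who stay in the study still have that visit.
- List the measurement in Table 1.
- Report the number tested out of the number exposed, with those who stopped before naltrexone began on day 8 shown separately so that they do not dilute the count for naltrexone.

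Any clinically indicated testing at the time of stopping, and the response to an abnormal value, stay with the study physician.

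The cost is a sentence in 6.3, a row in Table 1 and one reporting line, with no more than the two draws per NB starter already planned. The limits are that some early stoppers may decline, people who leave the study altogether may not be reached, and early stoppers' exposure will be shorter than a month, so their values should be read with the duration of exposure shown.
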